##### *d. Study outcomes/endpoints*

The study outcome will be a body of evidence that supports our hypothesis: that interactions with ADL content inside the graphical interactive virtual world, DevaWorld, supports completions of actual ADLs.

DevaWorld's feasibility (Aim 1)

Successful primary outcomes are >55% DWS-participation rate and a statistically significant difference between assessments of DWS-participation and non-participation, indicating tolerability and acceptability of routine DWS.

DevaWorld as an assistive tool for preparing and completing ADLs. (Aim2)

Successful secondary outcomes are:

- a reduction in ADL-related care challenges compared to baseline
- reduced time spent on ADLs compared to baseline
- a reduction in negative response behaviors associated with the ADL
- greater interest in the ADL
- a positive shift in care staff attitudes

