**Consent/No consent:**

As the app opens, the care staff will obtain verbal consent (resident uses affirming, positive words or sounds) or non-verbal consent (resident smiles/nods/leans toward the tablet/touches care staff in a positive way/agrees to touch the screen either independently with care staff's support).

If no consent, the caregiver will reapproach in 3-5 minutes, again check if the

person is comfortable, and make any adjustments to improve comfort. Care staff will seek consent again. If consent is not given a second time, the DWS will be dropped and the usual ADL routine will begin.

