**Ongoing Participation or Refusal:**

Staff will record the resident's attitude to the DWS in their daily report. The research team will review these reports daily.

Refusal may be communicated verbally (using negative or anxious words or sounds) or non-verbally (shrugging, shaking head, pushing the tablet away, refusing to put hand to the tablet, not permitting the care staff to hold their hand to support screen tapping, turning their body away, looking away from the app, passive disinterest

If a resident-participant decides that they no longer want to be involved in the study, not just the DWS session for the day, they will be offered DWS sessions daily. After 7 consecutive days of refusals, they will be withdrawn from the study.

(Guidance on the Process Consent method is covered during training and is described below.)

- Plan for 5 mins per session
- Upon consent, care staff initiates the DWS and guides the resident to the part of DevaWorld where the interactive ADL will be explored
- Following the resident's lead in pace and interest, the dyad focuses on helping the DevaWorld characters (male or female) to manage self-care activities in DevaWorld's bathroom and getting him/her ready for bed.
- The session will end when the resident seems ready
- Upon completion of a session, the care staff assists the resident, if needed, to select an emoticon on the end screen before ending the DWS.
- After completing the DWS, the care staff will initiate the planned ADL task, and observe their resident's interactions, cooperation, mood and any behavioral responses.
- Process Consent (21). This method is used during DevaWorld sessions.
  - Staff participant checks consent prior, during and after DW session.  
If Subject indicates their withdrawal of consent, Staff stops and lets the resident withdraw before or during the activity
  - If the resident no longer wants, or is no longer able, to be involved.  
The staff observes residents wishes (verbally or non-verbally) to guide the next steps. Staff then informs the researcher.
  - Depending on the situation, it may or may not be appropriate to ask the resident again later if they would like the opportunity to get involved., The caregiver will reapproach in 3-5 minutes, again check if the person is comfortable, and make any adjustments to improve comfort. Care staff will seek consent again. If consent is not given a second time, the DWS will be dropped and the usual ADL routine will begin.
- Assessments, tools  

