Training sessions will take place after baseline studies as knowledge transfer before or during baseline may introduce a bias. Staff will be shown the DevaWorld app and how to work optimally with it.

This will be a hands-on lesson with staff sharing one device between them alternating staff and resident roleplays. Mentia's instruction guide, 'How to get the most out of your DevaWorld Session' and training videos will be the basis of the training. Staff will also be guided on environmental aspects such as the best time and place, how to set up and introduce the DWS, and how to transition from the session to the ADL.

Each site will have a highly-trained internal champion, who will attend training and provide on-going support to staff throughout the study

Agenda for group training session.

- Introduction to the study aims and their critical role.
- Instruction on DevaWorld usage with a focus on the ADL content.
- A short review to identify any knowledge gaps.
- Follow-up sessions will be scheduled as needed.
- Break
- Study Protocol covering consent, scheduling, reporting, risks
- 5-minute pre-intervention interview so that we can learn about any potential barriers to participation in, or adherence to, clinical trial requirements.

iv. *Be clear about the difference between what is standard (if there were no evaluation study) and what is done specifically for the study.*

As a single arm study, the distinction we believe the distinction will be clear, i.e., care shift with usual care and the intervention, and care shift usual care and no intervention.

During the 6-week intervention part of study; on both intervention and no-intervention days, staff are encouraged to modify their practice according to any insights they derive from the study. They will be asked to note any modifications in their end-of-shift report.

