## IX. Analysis Plan

*Describe statistical analysis methods as appropriate. For example, will intention-to-treat methodology be used in the analysis? Will there be any sample stratification?*

- Thematic and sentiment analysis of tablet-recorded spoken and visual exchanges during DWS and post-session comments
- Statistical and text analyses of questionnaire responses
  - Statistical Analysis Plan
    - Assessment inventories with scores on the inventory's scale
    - Measuring mean value and standard deviation for the group
    - Complete a superiority statistical test
    - P-values calculated by t-test, 1 sided

HIPAA-compliant data capture software; eg REDCap, will be used to create the database and analyses. <https://www.project-redcap.org/>

Data will be reported graphically or with summary measure (e.g., means and standard errors or median and 95% confidence intervals), and subjected to statistical analysis when appropriate. Completion rates and grades scores will be presented as proportions and percentages.

ADCS-ADL scores will be compared from end of baseline to biweekly scores to the end of intervention and may be analyzed using a paired Student's t-test or the Wilcoxon signed-rank test if the data are not normally distributed.

Completion rates will be the percentage of all dyads who complete the entire eight weeks of study. The ratio of positively graded scores per dyad will be calculated to obtain the level of satisfaction of dyads and indicate the acceptability of DWS.

Aim 1: Successful primary outcomes are >55% completion rate and a statistically significant difference between assessments of completers and non-completers, indicating tolerability and acceptability of routine DWS.

Aim 2: The secondary outcome is to determine the feasibility of DevaWorld as an assistive tool for preparing and completing ADLs. Improved dyad outcomes are less time to complete ADLs, a reduction in negative response behaviors associated with the ADL, greater interest in the ADL, Care staff indicates tasks are easier than before.

Outcomes measures for baseline and intervention will be the same. As the score sheets cover a broader range of ADLs than those depicted in DW, overall and individual ADL scores will be analyzed and subjected to statistical tests. Our null hypothesis will be no statistical differences between ADL scores during the intervention and baseline phases

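### Half of the Aim 1 success rule is an undefined contrast, worded two ways; if days are split by whether the session was delivered, same-day mood can produce a difference with no DWS effect

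*Combined protocol and SAP*

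**What the plan says.** Section V.d gives Aim 1 two success conditions. The first is a rate: "Successful primary outcomes are >55% DWS-participation rate". The second is "a statistically significant difference between assessments of DWS-participation and non-participation, indicating tolerability and acceptability of routine DWS". It does not say whether the unit is a day, a session or a resident, which assessment is compared, or what counts as non-participation.

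Section IX restates Aim 1 with a completion rate in place of the participation rate, and with "a statistically significant difference between assessments of completers and non-completers, indicating tolerability and acceptability of routine DWS" as the contrast. Completion is defined per dyad: "Completion rates will be the percentage of all dyads who complete the entire eight weeks of study".

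Section VI.c.ii describes a refused session. Staff approach again after a few minutes. "If consent is not given a second time, the DWS will be dropped and the usual ADL routine will begin". As for signs, "Refusal may be communicated verbally (using negative or anxious words or sounds) or non-verbally"; the list goes on to turning away and passive disinterest. Staff report every day and rate attitude to the ADL from 1 to 4, so a refused day can still yield a rating.

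Section VI.c.iv describes two kinds of shift: "care shift with usual care and the intervention, and care shift usual care and no intervention". It does not say which kind a refused day is.

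**The concern.** A resident who is anxious or withdrawn on a given day is more likely to refuse the session, and is also more likely to be rated poorly at the ADL that follows. If days are sorted by delivery, one underlying state drives both the sorting and the rating. Accepted days are then better than average and refused days worse, whatever the session does.

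The contrast is half of the primary success rule. If a difference can be significant without any DWS effect, passing it says little about whether routine sessions are tolerated and accepted.

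**Working it through.** **The plan's own figures.** The plan gives no effect size, SD, refusal rate or power for this contrast. Its enrolment figure reproduces: 32/(1 − 0.20) = 40. The check uses the 32 evaluable residents.

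**Inputs from the documents.** Two sessions a week for six weeks give 12 scheduled DWS days per resident. Thirty weekdays less 12 leave 18 unscheduled days. The test is a one-sided t-test (section IX). A participation rate just above 55% allows refusal of just under 45%, if the denominator is offered sessions, which is not stated.

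**Assumptions.** Alpha is 0.05, one-sided. Refusal rate p is 10–45%. The day-level correlation r between mood and ADL rating is 0–0.5. There is no DWS effect.

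**Expected spurious difference, by hand.** Mood z is standard normal, and the resident refuses when z < q, where q = Φ⁻¹(p).
- Mean rating on accepted days: r·φ(q)/(1 − p).
- Mean on refused days: −r·φ(q)/p. Pooling these 12p days with 18 unscheduled days of mean 0 gives a comparator mean of −12·r·φ(q)/(12p + 18).

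At p = 0.20 and r = 0.3, φ(q) = 0.280:
- accepted: 0.3 × 0.280/0.80 = 0.105
- comparator: −12 × 0.3 × 0.280/20.4 = −0.049
- difference: 0.154 SD, of which 0.105 (68%) comes from accepted days

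At p = 0.45 and r = 0.3, φ(q) = 0.396:
- accepted: 0.3 × 0.396/0.55 = 0.216
- comparator: −12 × 0.3 × 0.396/23.4 = −0.061
- difference: 0.277 SD, of which 0.216 (78%) comes from accepted days

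The standard error at p = 0.20 is about √[(1/9.6 + 1/20.4)/32] = 0.069. Then 0.154/0.069 ≈ 2.2, against a critical value of about 1.65, so the false-positive rate is roughly 70%.

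**Simulation.** Settings: 32 residents, two randomly placed scheduled days a week, resident-level means, paired one-sided t-test, refusal wholly mood-driven, 1,500 runs per cell. False-positive rates (nominal 5%):

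| Comparison | r | 10% refused | 25% refused | 45% refused |
|---|---|---|---|---|
| Accepted vs all other days | 0 | 5% | 5% | 4% |
| Accepted vs all other days | 0.1 | 10% | 22% | 30% |
| Accepted vs all other days | 0.3 | 36% | 80% | 97% |
| Accepted vs all other days | 0.5 | 69% | 99% | 100% |
| Accepted vs refused only | 0.3 | 93% | 98% | 99.8% |
| Accepted vs unscheduled only | 0.3 | 19% | 53% | 84% |

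Scheduled versus unscheduled days, with refused days kept on the scheduled side, gives 3.7–5.8% in every scenario.

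**Weaker link between mood and refusal.** With refusal only partly mood-driven (assumed correlation 0.5 between mood and the tendency to refuse), accepted versus all other days gives about 29% at 20% refusal and 49% at 45% refusal for r = 0.3, and 7–15% for r = 0.1. If refusals also cluster in some residents (assumed between-resident SD 1.5), the r = 0.3 figures fall to 18% and 31%.

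**The case against.** A reader might infer that the plan puts refused days in the comparator, so that half the success rule is met by construction and bad days count against usual care. The documents do not support that.

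- Section V.d does not define non-participation. Section VI.c.iv answers a question about standard versus study procedures and is not an analysis rule; its mention of intervention and no-intervention days could equally mean days by schedule.
- Section IX, the only analysis section, uses a dyad-level contrast, to which the day-level calculation does not apply.
- The bias needs refusal to be linked to a worse rating. At zero correlation there is none, and the highest rates assume refusal wholly driven by mood. Selecting open, enthusiastic residents (section VI.a.iii) and the second approach after a comfort check may also lower refusal.
- The contrast is offered as evidence of tolerability and acceptability. The Aim 2 outcomes that name a comparator use baseline.

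All of this stands, and it limits the claim to a conditional one. It does not clear section V.d, which is current endpoint text with nothing in it to prevent the selection. The listed refusal signs overlap with what is rated at the ADL, so zero correlation is hard to defend. Nor is the completer reading safe: a resident who wants to leave and then refuses for seven consecutive days is withdrawn, so non-completers are partly defined by refusal.

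**Conclusion.** The point holds in conditional form. What is certain is that the second half of the Aim 1 success rule is undefined in section V.d and worded differently in section IX. If it is read as a day-level contrast by delivery, it is open to mood-related selection in favour of DWS, and no part of the plan removes this. Most of the bias (68–78% in the two worked cases) comes from accepted days being selected for good mood; refused days in the comparator supply the rest. Excluding refused days would therefore not cure it.

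The false-positive rate cannot be stated as one number. Over the assumed ranges it runs from the nominal 5% at zero correlation to almost certain rejection at high refusal and correlation. Neither input is given in the documents. On the completer reading the selection is between persons, and these rates do not describe it.

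**What to change.** 1. Reconcile sections V.d and IX, for both the rate (participation or completion) and the contrast.
2. Do not use participated versus not participated, or completers versus non-completers, as a success criterion for acceptability. Judge Aim 1 on the participation rate, with scheduled sessions stated as its denominator.
3. If a day-level ADL comparison is kept, classify days by the weekly DWS schedule set in advance: all scheduled DWS days, including refused ones, against scheduled non-DWS days, within resident. This controls the error rate only if scheduled days are set independently of mood. That needs stating, since section VI.c.ii lets staff spread sessions across their shifts.
4. Record scheduled, offered and refused on the daily report, and show refused days descriptively.
5. Reconcile the daily offers to residents who wish to leave with the two sessions per week, both in section VI.c.ii, because they change which days count as offered.

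The cost is wording and one item on an existing form. The downside is that refused sessions dilute the estimated effect of a delivered session. So does the encouragement in section VI.c.iv for staff to modify practice on both kinds of day.

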##### *c. Sample size determination and power analyses*

We target a 95% confidence level for our study. For a confidence interval of 15%, the sample size is 32. A 15% confidence level is sufficient for a feasibility study.

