  - ADL checklist: toothbrushing, grooming, face wiping, taking medications
  - Was the activity completed?
- Subject's responses to the ADLs (multiple choice and text box)
  - Subject's autonomy to the activity (Likert scale of 1- 4)
  - Subject's attitude to the activity (Likert scale of 1- 4)
- At the end of the baseline studies, staff complete an ADCS-ADL score sheet for

each of their residents to provide longitudinal comparisons (31).

- Data collected during the Intervention phase

Reporting on The DevaWorld App's Feasibility (Aim 1)

- The DW app captures screen interactions, durations, end-of-session emoticons for self-assessment and end-of-session comments (choice of spoken or text input).
- The tablet's built-in camera records the dyad's expressions and exchanges during the session. These videos support analysis of engagement and reaction, and create a unique data set for developing speech emotion recognition system for future product upgrades.
- Occasionally research staff may also capture video and audio using an iPhone during DWS for capturing other nuances of the dyad engagement.
- In addition, at end of shift, staff complete a web-based questionnaire that
  - measures tolerance and acceptance of DevaWorld
  - records observations of resident's post and pre-post disposition
- Questions are a mix of multiple choice, 5-point Likert scales and free text
- Computers are located at the nurse station.

Reporting on Usual ADLs, following Intervention (Aim 2)

- Staff's usual reporting at the end of each shift.
- Additional: the survey website.
  - Subject name
  - Which ADLs were done (checklist)?
  - Time taken to start and finish
- Subject's responses to the ADLs (multiple choice and text box)
  - Autonomy to the activity (Likert scale of 1- 4)
  - Attitude to the activity (Likert scale of 1- 4)
- End of study
  - Residents will repeat Quality of Life and Response Behavior outcome measures (same ones as used in Baseline).
  - Participating staff will complete an ADCS-ADL scores sheet for each of their residents to provide longitudinal comparisons
  - Participating staff will undertake a 5 min exit interview at the conclusion of the trial. The interview will supplement and facilitate the interpretation of quantitative data gathered during including any post and pre-post concerns over the course of the study, which may provide further insights (32).

*iii. Explain training of individuals performing procedures*

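### The significance half of the Aim 1 success rule names no deciding measure, so a chance favourable result on any one of several recorded measures can satisfy it

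*Combined protocol and SAP*

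**What the plan says.** Section V.d states the Aim 1 rule as a session participation rate above 55% together with "a statistically significant difference between assessments of DWS-participation and non-participation, indicating tolerability and acceptability of routine DWS". Section IX states it as "Successful primary outcomes are >55% completion rate and a statistically significant difference between assessments of completers and non-completers", and that sentence also goes on to say that the difference is to be read as a sign that routine sessions are tolerated and accepted. Neither gives a variable, a time point or a test.

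The general analysis text in section IX does not fill the gap. It lists "Assessment inventories with scores on the inventory's scale", a superiority test and "P-values calculated by t-test, 1 sided", and links none of these to the Aim 1 contrast. No test level is stated. The nearest figure is in section V.c, on sample size: "We target a 95% confidence level for our study".

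The plan records several measures that could be tested:

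- the per-dyad ratio of positive grades, which section IX treats as a sign of acceptability
- the end-of-shift questionnaire that "measures tolerance and acceptance of DevaWorld" (VI.c.ii, intervention-phase data for Aim 1)
- the resident's attitude to the session, entered in the daily staff report (VI.c.ii, ongoing participation or refusal)
- the daily ADL time, autonomy and attitude items (VI.c.ii, filed under Aim 2 in the intervention phase)

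**The concern.** The significance condition is the only inferential part of the primary success rule. With several eligible measures and none designated, the choice can be made after the data are seen. One measure could then meet the condition by chance while the others show nothing, and two analysts could reach opposite Aim 1 conclusions from the same data. The Background section says the evidence is meant to support the product's value in long-term care and its case for regulatory recognition. A success claim whose deciding variable was open at the time of analysis is weak support for either.

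**Working it through.** **Is there a plan figure to reproduce?** There is none for this condition: no error rate, power or multiplicity figure is given. The related figure is enrolment. 32 evaluable residents with 20% dropout gives 32 / (1 − 0.20) = 40, as stated in VI.a.i. The 32 rests on precision, not on power for this test.

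**Inputs for the error rate.**
- Test level: one-sided 0.05. This is an assumption, inferred from the 95% confidence level in V.c and the one-sided t-test in IX.
- Number of eligible measures, k: not given. The three daily ADL items alone give k = 3. Adding recorded attitude to the session and one acceptance measure gives k = 5. The ratio of positive grades and the acceptance items are counted once here, because the ratio may be built from those items.
- Correlation between measures, ρ: not given. Values of 0, 0.5 and 0.8 are shown.

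**Formula.** With independent measures, P(at least one false favourable result) = 1 − (1 − 0.05)^k:
- k = 3: 1 − 0.95³ = 0.143
- k = 4: 1 − 0.95⁴ = 0.185
- k = 5: 1 − 0.95⁵ = 0.226

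With correlation, Zᵢ = √ρ·C + √(1 − ρ)·Eᵢ, where C and the Eᵢ are standard normal. P(max Zᵢ > 1.645) was found by simulation with 400,000 draws.

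| k | ρ = 0 | ρ = 0.5 | ρ = 0.8 |
|---|---|---|---|
| 1 (named in advance) | 5% | 5% | 5% |
| 3 | 14.3% | 11.8% | 9.2% |
| 4 | 18.5% | 14.5% | 10.6% |
| 5 | 22.6% | 16.7% | 11.7% |

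At one-sided 0.025 with independent measures, the figures are 7.3% (k = 3) and 11.9% (k = 5), instead of 2.5%.

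**How much does the rate condition protect?** More than 55% of 40 means at least 23, since 22/40 is exactly 55%. The binomial probability of 23 or more out of 40 is:
- true rate 80%: 0.9997
- true rate 70%: 0.968
- true rate 60%: 0.689
- true rate 55%: 0.439

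The plan's 20% dropout implies 80% completion. At that rate the section IX version of the condition is almost certain to be met, so the significance test in effect decides Aim 1. The section V.d version uses a session participation rate, which the documents do not allow one to predict.

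**The case against.** The strongest reply is that the plan is less open than it looks. Section IX describes a per-dyad score and says that it indicates acceptability, which is what the Aim 1 difference is supposed to show. The rule also requires a difference that indicates tolerability and acceptability, and the tests are one-sided for superiority, so a favourable direction is intended. This is a single-arm feasibility study, and a chance result on one measure cannot deliver Aim 1 unless the rate condition is met too.

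Much of this stands, and it rules out several stronger readings that a reader might infer:

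- **That a worse score with DevaWorld would count as success.** The rest of the quoted sentence and the one-sided superiority test point the other way. What is missing is the link to a measure, and it matters because lower is better for ADL time while higher is better for a ratio of positive grades.
- **That chance alone can deliver Aim 1.** The rule has two joint conditions, and the percentages above apply to one of them.
- **That the tolerance and acceptance items cannot enter the contrast because they have no value without participation.** A session can be offered and refused, and staff record the attitude to it. A resident who leaves after sessions have begun can also have such data.
- **That the baseline GDS, FAST and MMSE add to the count.** They precede any session and cannot show whether sessions are tolerated.
- **That the ADL response entry is a further measure.** It reads as a heading over the autonomy and attitude items, and it has no stated score.

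The ratio of positive grades is the most natural candidate, but section IX does not name it as the variable to be tested. The feasibility label does not remove the problem either, because the sponsor chose a significance test as a primary success condition.

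**Conclusion.** The point holds for the significance condition of the Aim 1 rule, in both V.d and IX. No deciding measure is designated, the implied favourable direction is not tied to one, and no alpha, hierarchy or multiplicity control limits the choice. Assuming one-sided 0.05 and 3 to 5 eligible measures, the chance of at least one false favourable result is about 9% to 23% (about 12% to 17% at correlation 0.5), against 5% for a single named measure. The test level, the count and the correlations are assumptions, so this is a range and not an estimate for this trial. It is not the false-positive rate of Aim 1 as a whole, which also depends on the rate condition.

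**What to change.** In V.d and IX:

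1. Name one Aim 1 measure and its favourable direction as the sole deciding variable. One example is section IX's per-dyad ratio of positively graded scores, higher being better. State which items are graded and what counts as positive. The daily attitude-to-activity item is a poorer choice, because it measures attitude to the ADL and belongs to Aim 2.
2. Reconcile the contrast. V.d compares participation with non-participation, and IX compares completers with non-completers. The chosen measure must be defined on both sides of whichever contrast is kept.
3. State the alpha.
4. State that all other assessments in this contrast are descriptive and cannot satisfy the Aim 1 criterion.

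This returns the false favourable rate of the condition to the stated level. Keeping five measures at 0.05/5 = 0.01 each would also control it (1 − 0.99⁵ = 0.049), but at a cost in power. With 32 completers and 8 non-completers, the plan's own 20% dropout, a one-sided t-test has about 80% power for a difference of 1.0 SD at 0.05 and about 55% at 0.01. Even the single test has only 34% power at 0.5 SD, which the sponsor should know before keeping a significance condition.

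The cost is a few sentences and no new data. The downside is that the sponsor can no longer rely on whichever measure happens to be significant.

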### **I. Abstract - Summary of the study background, aims, and design.**

Central themes in person-centered care are dignity/respect/choice for the care recipient.

This SBIR Phase 1 clinical study is a minimal risk study that focuses on how the new technology, DevaWorld (DW), can support and amplify these principles, while assisting care staff.

DevaWorld is an interactive assistive technology developed with user-centered design principles, mirroring fifteen evidence-based non-pharmacological interventions for people living with Alzheimer's disease and its related dementias (AD/ADRD). Built with a game engine and deployed on a tablet device, DevaWorld is a purpose-built virtual world depicting activities of daily living (ADLs). It contains interactive engagement stimuli, including customized digital artifacts that hold meaning to the person.

During a DevaWorld session (DWS), both the care-partner and care-receiver (dyad) are active participants. Preliminary evidence shows that DWS sessions support the psychosocial wellbeing of people living with dementia (PLWD). Informally collected data lead us to the current study, in which we measure the impact of DevaWorld ADLs on actual ADLs. We hypothesize that undertaking ADL-related virtual activities will support completions of actual ADLs, thereby increasing effectiveness and improving care outcomes.

The aims of this mixed-method, single-arm study are to (1) demonstrate the feasibility (tolerability and acceptability) of DevaWorld within daily routines, and (2) evaluate the effectiveness of DevaWorld sessions in preparing PLWD for specified ADLs. Endpoints are: evidence of the dyads' acceptance of DevaWorld, a reduction in ADL-related care challenges compared to baseline, and overall durations of time spent on the ADLs compared to baseline.

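### Aim 2 success is defined by direction alone: no test result is a condition of it, and the only stated null hypothesis is on a score in neither Aim 2 list

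*Combined protocol and SAP*

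**What the plan says.** Section V.d gives five Aim 2 criteria under "Successful secondary outcomes are":

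1. "a reduction in ADL-related care challenges compared to baseline"
2. "reduced time spent on ADLs compared to baseline"
3. "a reduction in negative response behaviors associated with the ADL"
4. "greater interest in the ADL"
5. "a positive shift in care staff attitudes"

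None carries an instrument, a size of change, a test or an alpha, and nothing says whether one, several or all must be met. Aim 1, directly above, needs a rate over 55% and a significant difference.

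Section IX restates Aim 2 as four directional items. Care challenges are gone, and the staff-attitude item has become staff reporting that tasks are easier. The section also names a superiority test with one-sided t-test p-values for questionnaires and inventories, gives no alpha, and does not link the test to any Aim 2 item. It closes with: "Our null hypothesis will be no statistical differences between ADL scores during the intervention and baseline phases". The preceding sentence is about score sheets, and the data-collection list in VI.c.ii shows that these are the ADCS-ADL sheets.

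The abstract's ADL endpoints are care challenges and "overall durations of time spent on the ADLs compared to baseline". ADCS-ADL is not named there.

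**The concern.** A success criterion should be one that the study can fail. Here the criteria are directions, and the one variable with a stated null hypothesis is outside both lists of criteria. No sentence makes any test result a condition of Aim 2 success. A reader applying V.d as written could call Aim 2 successful on a small favourable shift whatever the ADCS-ADL comparison shows.

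This matters because section III states the primary objective in Aim 2 terms (virtual ADLs supporting real ones), and section II says the evidence will be used to support the product's value in long-term care and its regulatory case. The difference between the V.d and IX lists also leaves room to choose the list after the results are known.

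**Working it through.** The plan gives no figure for Aim 2 success, so there is none to reproduce. The check asks how often the criteria would be met by chance under each combination rule that the text allows.

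**Inputs.** Five items (V.d) or four (IX). Assumed: no effect, each item 50% likely to move favourably, and a common correlation between items of 0, 0.3, 0.5 or 0.8. For the tested case, alpha is assumed, because IX gives none; the nearest figure is the 95% confidence level in V.c. The evaluable sample is 32 (V.c).

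**Direction only, five independent items.**
- At least one: 1 − 0.5^5 = 0.969
- At least three: (10 + 5 + 1)/32 = 0.500
- At least four: (5 + 1)/32 = 0.188
- All five: 0.5^5 = 0.031

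**Direction only, correlated items** (simulation of equicorrelated normal variables, 2,000,000 draws).

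| Correlation | At least one | At least three | All five |
|---|---|---|---|
| 0 | 96.9% | 50.0% | 3.1% |
| 0.3 | 89.6% | 50.0% | 10.4% |
| 0.5 | 83.3% | 50.0% | 16.7% |
| 0.8 | 71.0% | 50.0% | 29.1% |

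Correlation lowers the any-one figure and raises the all-five figure. The majority figure stays at 50% by symmetry.

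**Four items of section IX, independent.** At least one: 1 − 0.5^4 = 0.938. All four: 0.5^4 = 0.063.

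**If each of the five were tested.** At one-sided 0.05, the chance of at least one significant result is 1 − 0.95^5 = 0.226 if independent, and 0.117 at correlation 0.8. At one-sided 0.025 it is 1 − 0.975^5 = 0.119 if independent. With 0.05/5 = 0.01 per item it is 1 − 0.99^5 = 0.049. Adding tests without a combination rule therefore reduces the problem but does not remove it.

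**What one tested outcome would demand.** With n = 32, a paired one-sided 0.05 test needs an observed standardised mean change of at least t(0.95, 31)/√32 = 0.30. The present wording accepts any change above zero.

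**The case against.** Section V.d lists outcomes and section IX holds the methods, so it can be said that the tests are there. The general one-sided t-test could well cover some items: response behaviours through the NPI, repeated at end of study, or ADL time and attitude through the daily survey. This stands, and it would be wrong to say that the plan has no test for the listed items. What is missing is an alpha, a link from test to item, and a statement that success depends on the result.

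A reader might infer that the ADCS-ADL test decides nothing. The documents do not go that far. The null hypothesis comes soon after the Aim 2 paragraph and may be meant as the Aim 2 hypothesis, and the sponsor may intend ADCS-ADL as the measure of care challenges, which have no named instrument. Neither link is written down.

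A reader might also take 97% as the false-success rate. That needs both independence and a rule that any one item suffices. The plan states no such rule, and independence is unlikely when the same staff report most items on the same residents.

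Finally, these are secondary outcomes of a single-arm feasibility study, and V.d speaks of evidence taken together rather than a formal pass or fail. That lowers the stakes. But the same section uses the language of success and gives Aim 1 a firm rule, so the absence of one for Aim 2 is a real gap.

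**Conclusion.** The point holds in this form: Aim 2 success is directional, has no combination rule, depends on no test result, and is not linked to the only stated null hypothesis. Under no effect, the chance of meeting the criteria is about 71–97% (any one item), 50% (majority) or 3–29% (all five). The width of that span is itself the finding, since the plan does not say which rule applies.

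The figures rest on the assumed 50% per item and the assumed correlations of 0 to 0.8. Ties on the four-point scales would lower the 50%. Selecting residents for ADL challenges in the previous month (VI.c.i) could raise it through regression to the mean. The documents do not show that the sponsor intends the any-one reading or would disregard a negative ADCS-ADL result. The study can run as designed, but its Aim 2 verdict could not be interpreted as the criteria stand, so the change should be made.

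**What to change.** Change the wording of V.d and IX before data are seen:

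- **Name one Aim 2 decision outcome measured in both phases.** The choice is the sponsor's. ADL time is a candidate because it is in the abstract, V.d and IX. Its drawback is that the objective in section III is more manageable and effective completion, not faster completion. If it is chosen, align the time fields of the two survey forms, which are worded differently, and say which intervention days count. ADCS-ADL is another candidate if V.d lists it as an Aim 2 outcome; its schedule then needs settling, since IX mentions biweekly scores and VI.c.ii lists only baseline and end-of-study sheets.
- **State the null hypothesis on that outcome, with an explicit alpha and sidedness.** Require the matching confidence interval to exclude no change before Aim 2 is called successful.
- **Report the remaining outcomes as supportive estimates with 95% confidence intervals**, each mapped to an instrument. Care challenges have none now, and the staff attitude questionnaire is scheduled only at baseline in VI.c.ii.
- **Make the V.d and IX lists agree.**

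The core change needs no additional residents. The price is fewer routes to a success claim and a criterion that can fail: with 32 residents and a one-sided 0.05 test, power is about 51% for a true standardised change of 0.3 and 87% for 0.5.
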